### **AESI monitoring and Safety Visit**

To monitor potential spread of toxin, the subject (if applicable) and/or parent(s) or caregivers (if applicable) will be actively questioned for the occurrence of AESIs at each visit or Telephone Contact [TC] starting with Baseline Visit of MP (V2). If a TC identifies an (S)AE/AESI that needs confirmation or treatment (e.g., respiratory disorder, dyspnoea, aspiration, dysphagia, speech disorder, dysphonia, other signs of bulbar palsy or botulism), the investigator must schedule a Safety Visit [SV] in addition to scheduled visits as soon as possible after the Telephone Contact. SV are unscheduled extra visits for assessment of (S)AE/AESIs only.

[figure not shown]
If a subject withdraws from participation during the study at any point of time, every attempt should be made to conduct the assessments foreseen for the End of Study Visit (V17).

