Any subject who discontinues from the study due to AEs will be treated according to standard clinical strategies. All pertinent information concerning the AE will be documented in the subject's file as well as in the eCRF AE report form (and in addition in an SAE or AESI report form, if applicable).

Following discontinuation, a final examination (End of Study Visit) should be performed for safety reasons. However in a pregnant female no invasive assessments, e.g., blood sampling should be performed. The pregnancy has to be followed up until the date of delivery (see also [Section 10.4](#)). The investigator is required to make every effort to contact the subject (if applicable) or parent(s) lost to follow-up, and all such efforts should be documented in the subject's file (e.g., times and dates of telephone contact, copies of letters).

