#### *9.1.1.5 Investigator's Global Assessment of Tolerability*

The Investigator's Global Assessment of Tolerability is an estimation made at the end of treatment cycles in MP and OLEX. This evaluation bases on a 4-point ordinal scale proved useful in several phase 3 clinical studies conducted with NT 201 (see IB for additional information [[Merz Pharmaceuticals \(GmbH\) - IB](#)]).

The global assessment will be made on the following 4-point ordinal scale (see [Table 16](#) and [Table 17](#)):

- 1 = very good.
- 2 = good.
- 3 = moderate.
- 4 = poor.

The investigator will assess the scale at the Final Visit of MP V5, the End of Cycle Visits V9 and V13 and at the End of Study Visit (V17).

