6.5.3 Other Safety Variables

Other safety variables of the MP comprise:

- Investigator's Global Assessment of Tolerability at the Final Visit of MP V5 (In the definition of this variable the visit number was added.)
- Vital signs (blood pressure, heart rate) at all visits of MP
- Body Mass Index (BMI), weight and height at Screening V1, Baseline Injection Visit V2, at the Final Visit of MP V5
- Clinical chemistry, differential count and hematology at Screening V1
- Occurrence of antibodies against BoNT-A in subjects ≥ 21 kg BW at Screening V1
- Number of subjects with suicidal ideation, suicidal behavior, and self-injurious behavior without suicidal intent based on the Columbia-Suicide Severity Rating Scale (C-SSRS) This scale is used to assess suicidality prospectively in this clinical study at baseline and all post-baseline visits of the MP.

Other safety variables of the OLEX comprise:

- Investigator's Global Assessment of Tolerability at Day 99 (Week 14) of all OLEX cycles, i.e. at End of Cycle Visit (V9, V13) and at End of Study Visit (V17). In the definition of this variable the visit numbers were added.
- Vital signs (blood pressure, heart rate) at all visits of OLEX period (V6, V7, ..., V17). In the definition of this variable the visit numbers were added.
- BMI, weight and height at all Injection Visits of OLEX (V6, V10 and V14) and at the End of Study Visit (V17). If V5 and V6 will be performed at the same day, BMI, weight and height can be transferred from V5 to V6.
- Clinical chemistry, differential count and hematology at the Injection Visit V6 of OLEX and the End of Study Visit (V17).
- Occurrence of antibodies against BoNT-A in subjects ≥ 21 kg BW at the End of Study Visit (V17). In the definition of this variable the visit numbers were added.
- Number of subjects with suicidal ideation, suicidal behavior, and self-injurious behavior without suicidal intent based on the Columbia-Suicide Severity Rating Scale (C-SSRS) This scale is used to assess suicidality prospectively at all OLEX visits.

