Laboratory data, unscheduled and doubly performed laboratory data will be listed individually. For additionally performed laboratory measurements of certain subjects on other visit dates or of other laboratory parameters than planned no descriptive statistics will be created.

If subjects have additional laboratory examinations during screening examination, only the last sample before application of study medication will be used for final analysis tables. No post-baseline laboratory data is planned for the MP.

Vital signs, body weight, height, and BMI

The individual blood pressure, heart rate, body weight, height, and BMI data will be listed and summarised (n, mean, standard deviation, minimum, 1st quartile, median, 3rd quartile and maximum) at each time point. Descriptive statistics will be given for absolute values and changes from baseline V2.

Frequencies of subjects with lowered, normal, or raised values will be displayed as shift tables from Baseline V2 vs. Control Visits V3, V4, and Final Visit V5.

High and low values are defined as given in Table 4.

Table 4: High and Low Values of Vital Signs

Vital Sign Variable	Flag	Observed Value
Systolic Blood Pressure (mmHg)	High	≥ 180
	Low	≤ 90
Diastolic Blood Pressure (mmHg)	High	≥ 105

Vital Sign Variable	Flag	Observed Value
Heart rate (bpm)	Low	≤ 55
	High	≥ 110
Height (cm)	High	Not applicable
	Low	Not applicable
Weight (kg)	High	Not applicable
	Low	Not applicable
BMI (kg/cm ²)	High	≥ 30
	Low	≤ 18.5

A value is considered as high/low if it meets the criterion for observed values

Botulinum Toxin Antibodies

For the subset of subjects with body weight greater or equal to 21 kg, frequency tables will be presented for Screening V1 by category (Fluorescence Immuno Assay for antibodies (FIA-AB)/Hemi diaphragm assay (HDA)), treatment group, pre-treatment status (treatment-naïve/pre-treated, i.e. pre-treatment with any BTX for any indication).

Investigator’s Global Assessment of Tolerability

Frequency tables and descriptive statistics will be generated for the data collected at Final Visit V5 of the Main Period.

The following analyses will be performed for the OLEX data:

C-SSRS

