For the subset of subjects with body weight greater or equal to 21 kg, frequency tables and shift tables for Screening vs. End of Study Visit (V17) will be presented by category (Fluorescence Immuno Assay for antibodies (FIA-AB)/Hemi diaphragm assay (HDA)), treatment group, pre-treatment status (treatment-naïve/pre-treated, i.e. pre-treatment with any BTX for any indication).

Investigator's Global Assessment of Tolerability

Frequency tables and descriptive statistics will be generated for the data collected at Day 99 (Week 14) of all OLEX cycles.

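### The SAP summarises main-period tolerability only at V5, so ratings from children who withdraw earlier enter no summary table, and it has no clear rule for mid-cycle withdrawals in the extension.

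*SAP*

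**What the plan says.** Protocol section 9.1.1.5 states: "The Investigator's Global Assessment of Tolerability is an estimation made at the end of treatment cycles in MP and OLEX". It schedules the rating at V5 and then at "the End of Cycle Visits V9 and V13 and at the End of Study Visit (V17".

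For withdrawal at any time, Protocol section 6.1 (under AESI monitoring and Safety Visit) says "every attempt should be made to conduct the assessments foreseen for the End of Study Visit (V17". Protocol section 7.3.1 adds: "Following discontinuation, a final examination (End of Study Visit) should be performed for safety reasons".

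SAP section 6.5.3 defines the MP variable as the "Global Assessment of Tolerability at the Final Visit of MP V5". Section 7.5.3 tabulates it in the same way: "Frequency tables and descriptive statistics will be generated for the data collected at Final Visit V5 of the Main Period". For OLEX, section 6.5.3 ties the variable to Day 99 of each cycle and then to visit labels ("i.e. at End of Cycle Visit (V9, V13) and at End of Study Visit (V17"), while the analysis sentence in section 7.5.3 refers to "data collected at Day 99 (Week 14) of all OLEX cycles". SAP section 7.5 runs OLEX safety analyses on the OLEX safety evaluation set, which under section 5 requires at least one OLEX injection.

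**The concern.** The protocol produces tolerability ratings at early End of Study Visits, but the SAP has no place for them. Protocol section 7.3.1 requires discontinuation for certain severe adverse events of special interest and for any adverse event that makes continuing too risky. A poor rating is plausible in just those children. If their ratings are left out, the MP table describes only children who stayed to V5. If leavers rate worse, it will look more favourable than the collected data.

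In OLEX the concern is the trend over repeated injections. A rating made after a cycle 2 or cycle 3 injection should be read with that cycle. It should neither count towards cycle 4 nor be dropped.

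**Working it through.** The plan states no figure for this variable, so the check is mainly a trace of the text, followed by an illustration on assumed rates.

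**Child who leaves MP before V5**

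1. The End of Study assessments are to be done (Protocol 6.1 and 7.3.1), and they include tolerability (Protocol 9.1.1.5). A rating should exist.
2. The MP table takes V5 only (SAP 6.5.3, 7.5.3). The rating was not made at V5.
3. The OLEX table uses the OLEX safety set (SAP 7.5). The child had no OLEX injection and is not in it.
4. The rating enters neither summary.

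**Child who leaves mid-cycle in OLEX cycle 2 or 3**

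1. An early End of Study rating exists, with none at V9 (cycle 2) or V13 (cycle 3).
2. Read by visit label (SAP 6.5.3), it falls under V17, which SAP 3.1 places at Day 99 of the 4th cycle.
3. Read by nominal day (SAP 7.5.3), a rating well before Day 99 of the current cycle belongs to no cycle.
4. The SAP does not choose between these readings, and neither puts the rating in the cycle in which the child stopped.

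**How the SAP treats comparable data.** Section 7.5.2 allocates TEAEs to the cycle of the preceding injection. Section 7.6 computes observation period and cycle length from the last available visit when no further injection follows. The missing-data rules in 7.7.1 concern efficacy, and section 8 lists no mapping for tolerability.

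**Illustration.** The only drop-out figure in the documents is 3% in comparable studies at the time of the primary assessment (SAP section 4), which is Week 4 here. Assume that a share *d* of those injected leaves mid-cycle in each cycle, that all leavers are rated, and that all others continue. Start from N = 344.

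| Quantity | Formula | d = 3% | d = 5% | d = 10% |
|---|---|---|---|---|
| MP ratings outside V5 | 344·d | 10.3 | 17.2 | 34.4 |
| Enter OLEX | 344·(1−d) | 333.7 | 326.8 | 309.6 |
| Leave in cycle 2 or 3 | 344·(1−d)·[1−(1−d)²] | 19.7 | 31.9 | 58.8 |
| Injected in cycle 4 | 344·(1−d)³ | 314.0 | 294.9 | 250.8 |
| Share of V17 rows not from cycle 4 (label reading only) | 1−(1−d)² | 5.9% | 9.8% | 19.0% |

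For one arm of 172, assume 2 poor ratings among those who reach V5 and *w* leavers, all rated poor. The V5 table shows 2/(172−w), and all collected ratings give (2+w)/172.

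- w = 2: 2/170 = 1.2% against 4/172 = 2.3%.
- w = 8: 2/164 = 1.2% against 10/172 = 5.8%.

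The counts of poor ratings have no source in the documents. They show only how the rule works.

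**The case against.** **Tolerability by dose is not lost.** A reader might infer that the V5 rule removes the only randomised comparison of tolerability. It does not. TEAEs, TEAEs of special interest, serious TEAEs, worst intensity and TEAEs leading to discontinuation are analysed by MP dose group on the full MP safety set (SAP 6.5.2, 7.5, 7.5.2). A child withdrawn for severe dysphagia is counted there. This stands: what is missing is one summary rating, not the safety signal.

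**Display as cycle 4 is not established.** A reader might also infer that OLEX leavers are certainly shown as cycle 4. The analysis sentence is worded by Day 99 of each cycle, and the protocol asks for the V17 assessments without stating that the early visit carries the number V17. SAP 7.6 names V17 as the example for completers. This stands: cycle 4 is one of two readings.

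**Few children may be affected.** Those who end at V5, V9 or V13 because reinjection is not needed already have their rating. MP has a single injection, so reaching V5 needs no further treatment. This also stands: only withdrawals before the end-of-cycle visit matter.

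**V5 only follows the protocol.** Protocol 12.3.5.3 defines the variable at Day 99, and a rating after three weeks differs from one after 14. That is a reason to flag early ratings. It does not justify leaving them out of every summary when the protocol asks for them.

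**The mapping may be elsewhere.** The contents of Protocol Tables 16 and 17 and of the SAP's list of tables are not in the available text. A rule there, or an individual listing of these ratings, cannot be excluded.

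**Conclusion.** The gap is real but narrow. On the available text, a tolerability rating from a child who leaves before V5 enters neither the MP nor the OLEX summary table, so the by-dose summary of this scale is restricted to children who reached V5. For mid-cycle OLEX withdrawals the SAP is inconsistent between visit label and nominal day, and neither reading is satisfactory.

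The consequence is confined to a descriptive scale and touches neither type I error, power nor any confirmatory test. The MP table would look too favourable if leavers rate worse than those who stay. A distorted comparison between doses would further require that leaving, or the leavers' ratings, differ by arm, which the documents do not show. The size is unknown. The illustrative 10 to 34 MP ratings, and 6% to 19% of V17 rows under the label reading, rest on assumed withdrawal of 3% to 10% per cycle with every leaver rated.

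**What to change.** In SAP 6.5.3 and 7.5.3, assign each tolerability rating to the cycle of the most recent injection:

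- MP: V5, or the early End of Study rating if the child left before the first OLEX injection.
- OLEX cycles 2, 3 and 4: V9, V13 and V17 respectively, or the early End of Study rating if the last injection was in that cycle.

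Show early-termination ratings as a flagged or separate row, because they cover less than 14 weeks of observation. This keeps the Day 99 summary visible alongside the fuller one.

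The rule follows the SAP's own allocation of TEAEs. It costs a few lines of text and one derivation, needs no new data, and should be in place before the MP blind is broken. If the table shells already contain such a mapping, a cross-reference is enough.

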## 9 STUDY ASSESSMENTS AND VISIT SCHEDULE

### 9.1 Assessments

The following efficacy and safety assessments will be performed during this double-blind, randomized, parallel-group three arm dose-response study. The assessments on the AS used as efficacy variables will be performed by trained investigators only (see [Sections 9.1.1.1](#) and [9.1.1.2](#)). The assessment of AS must be performed after the assessment of GICSSs at week 4 of all treatment cycles of MP and OLEX. On days of injection visits, all assessments have to be performed prior to injection treatments. For standardization of laboratory test results, a central laboratory will analyze blood samples in this multi-center study.

An overall description of the study plan is provided in [Section 6.1](#) and in the Flow Chart in [Section 6.1.2](#). The time schedule of assessments is detailed in [Section 9.2](#). A tabular overview of study assessments is given in [Table 16](#) and [Table 17](#).

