In case eligibility criteria for reinjection are not fulfilled at a scheduled visit (Final Visit of MP or End of Cycle Visits V9 and V13) at the end of an treatment cycle, the Injection Visit of the following treatment cycle can be postponed and rescheduled within up to 16 weeks after the previous injection treatment (for details see [Section 6.1](#))

[figure not shown]
Attempt should be made to arrange all visits at the same day time for an individual subject (i.e., morning or afternoon) to standardize treatment and assessment conditions. The End of Study Visit will be at Week  $14 \pm 2$  weeks (Day  $99 \pm 14$  days) of 4th treatment cycle. Study activities and visit schedule are detailed in [Table 16](#) and [Table 17](#).

[figure not shown]
---

 If the Final Visit of MP and the 1st Injection Visit of OLEX will be performed on the same day the results of these assessments can be transferred from V5 to V6.

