7.5.2 Secondary Safety Variables

Adverse events

AEs will be coded according to the Medical Dictionary for Regulatory Activities (MedDRA, version 21.0). For MP, only treatment emergent adverse events (TEAEs) of the MP will be analyzed, which are defined as AEs with onset or worsening on or after date and time of the first MP administration and before date and time of the first OLEX administration at V6. For subjects who do not receive an OLEX administration all AEs with onset or worsening on or after date and time of the first MP administration will be considered as TEAEs of MP. TEAEs of the OLEX are defined as AEs with onset or worsening at or after date and time of the first OLEX administration at V6. TEAEs will be allocated to an injection cycle x in the OLEX Period, if adverse events has onset or worsening on or after injection x and before injection x+1 (if applicable). TEAEs of the OLEX will be analyzed in total and per treatment cycle. Additionally TEAEs of the MP and the OLEX period will be displayed together in total.

Only TEAEs will be analyzed. Non-TEAEs will only be listed.

If an AE worsens between start and end of this AE it will be considered as new AE starting with the date of the worsening. In this case the imputation of end dates within episodes of the

same AE will be done by setting the end date/end time to start date/start time of the consecutive worsening record.

In detail missing or partially missing start and stop dates of an AE will be imputed as follows for the calculation of the duration of an AE:

- if start time is missing and start date is given and not equal to date of an injection visit, set start time to 00:00, else if start date is equal to date of an injection visit set start time to time of injection, if given (else 00:00)
- if start date/time is completely missing and end date is before first exposure in the MP: no imputation
- if start date/time is (partially) missing and end date after or equal first exposure in the MP or missing:
 - only start day is missing, but start month and start year same as an injection visit: set start day and start time to day and time of this injection visit, else set start day to 1 and start time to 00:00
 - start day and start month are missing, but start year is the same as year of first exposure in the MP: set start day, start month, start time to day, month, time of first exposure in the MP, else set start day and start month to 1 and start time to 00:00

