7.5.3 Other Safety Variables

Laboratory evaluations, vital signs, BMI, body weight, height, Investigator’s Global Assessment of Tolerability, and incidences of subjects with antibodies against BoNT-A will be analyzed descriptively (values and changes from baseline) and screened for individual notable values and/or changes. Results of the C-SSRS will be summarized descriptively.

The following analyses will be performed for the MP data:

C-SSRS

Additionally, to fulfill FDA requirements, prospective monitoring of suicidality with the C-SSRS should be considered the most important (but not the only) source of information concerning suicidality.

These C-SSRS assessments will be done in the subpopulation of subjects enrolled after amendment 1.0 approval only.

Suicidality will be assessed prospectively in subjects at baseline and all post-baseline visits. The appropriate version of this scale ensures the consistent application of this important measure regardless of indication or investigator experience with the subject matter. With C-SSRS in place, administration of this semi-structured clinician-based assessment scale is standardized. The C-SSRS quickly and efficiently identifies those subjects that require additional clinician follow up.

Following versions of the C-SSRS are to be applied only for subjects enrolled after amendment approval:

1. Children's baseline / screening version
2. Children's since last visit version.

The C-SSRS interview should only be assessed with children of respective age and cognitive state. Clear age cut-offs for the C-SSRS were not defined by the authors, but it has been found that administration is possible in general for children with a developmental age of about 7 years. Otherwise it should be documented in the eCRF that a child was not able to assess the C-SSRS at a respective visit.

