The C-SSRS is based on the research and development at the Columbia University by Posner et al. [Posner 2007a (3)] supported by Columbia-Classification Algorithm for Suicide Assessment (C-CASA) developed by the same group [Posner 2007b (4)]. It is a semi-structured clinical interview consisting of domains of suicidal ideation, suicidal behavior and non-suicidal self-injurious behavior, and details of actual and potential lethality. It is designed for personal interview administration. Subjects or Parents/Caregivers are asked directly by a trained clinical assessor. Clinical assessment questions are presented, and subjects provide their responses. These responses enable the interviewer to branch to the appropriate follow up questions, faithfully adhering to C-SSRS probing specifications and potential positive responses. This approach provides consistent assessment and documentation.

At the end of the assessment the subject should not be released from the study center until the results of the C-SSRS (positive or negative) are reviewed and the subject is not considered to be at risk. If there is doubt about whether a subject is at risk, the Investigator should obtain appropriate psychiatric consultation.

For the sub-population of subjects enrolled after amendment approval and of respective age and cognitive state the following analysis will be performed. Descriptive frequency tables will be displayed for total sub-population and by treatment group. The number of subjects who experience any suicidal ideation, suicidal behavior, or self-injurious behavior without suicidal intent at least once at any post-baseline visit of the Main Period will be tabulated. Statistical evaluation of the data will be performed according to Table 1 of the Columbia–Suicide Severity Rating Scale Scoring and Data Analysis Guide Version 2.0 (Finalized February 2013) [Nilsson 2013 (5)]. Baseline data and further C-SSRS data such as intensity of ideation and lethality data will only be listed.

Laboratory data

Descriptive statistics for absolute values at Screening V1 will be given for continuous variables. No categorical laboratory variables will be collected. Laboratory parameters will be sorted by predefined categories (e.g., hematology, differential count, and chemistry).

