For the sub-population of subjects enrolled after amendment 1.0 approval and of respective age and cognitive state the following analysis will be performed. Descriptive frequency tables will be displayed for total sub-population and by MP treatment group. The number of subjects who experience any suicidal ideation, suicidal behavior, or self-injurious behavior without suicidal intent at least once at any visit of the OLEX will be tabulated. Statistical evaluation of the data will be performed according to Table 1 of the Columbia–Suicide Severity Rating Scale Scoring and Data Analysis Guide Version 2.0 (Finalized February 2013) [Nilsson 2013 (5)]. Further C-SSRS data such as intensity of ideation and lethality data will only be listed.

Laboratory data

Descriptive statistics for absolute values at the Injection Visit V6 and the End of Study Visit (V17) and changes from Screening V1 to V6 and to V17 will be given for continuous variables.

The number of subjects with lowered, normal, or raised values compared to normal range as shift tables from Screening V1 vs. V6 and V1 vs. V17. Laboratory parameters will be sorted by predefined categories (e.g., hematology, differential count, and chemistry).

Laboratory data, unscheduled and doubly performed laboratory data will be listed individually. For additionally performed laboratory measurements of certain subjects on other visit dates or of other laboratory parameters than planned no descriptive statistics will be created. If subjects have additional laboratory examinations during screening examination, only the last sample before treatment start will be used. The first valid value for a post-baseline visit is analyzed.

Vital signs, body weight, height, and BMI

The individual blood pressure, heart rate, body weight, height, and BMI data will be listed and summarised (n, mean, standard deviation, minimum, 1st quartile, median, 3rd quartile and maximum) at each time point. Descriptive statistics will be given for absolute values and changes from baseline V2.

Frequencies of subjects with lowered, normal, or raised values will be displayed as shift tables from Baseline V2 vs. all available OLEX period visits.

Botulinum Toxin Antibodies

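### The open-label suicidality table counts the V6 interview, which precedes the first open-label injection and describes time the SAP elsewhere assigns to the Main Period

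*SAP*

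**What the plan says.** For the OLEX, SAP 7.5.3 tabulates subjects with suicidal ideation, suicidal behaviour or "self-injurious behavior without suicidal intent at least once at any visit of the OLEX will be tabulated". For the MP, the same section counts subjects positive "at least once at any post-baseline visit of the Main Period will be tabulated", which leaves out the interview before the first study injection. The OLEX sentence has no such limit.

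On timing, SAP 6.5.3 says of the C-SSRS in the OLEX: "This scale is used to assess suicidality prospectively at all OLEX visits". SAP 3.1 lists V6 as an OLEX injection visit, and the vital-signs entry in SAP 6.5.3 numbers the visits in the same way: "at all visits of OLEX period (V6, V7, ..., V17". After baseline the form is the "Children's since last visit version" (SAP 7.5.3). Protocol 9.1 gives the general rule: "On days of injection visits, all assessments have to be performed prior to injection treatments".

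For adverse events, SAP 7.5.2 starts the OLEX later. An event is an OLEX TEAE only with "onset or worsening at or after date and time of the first OLEX administration at V6"; anything between the first MP injection and that moment is an MP TEAE. SAP 7.6 likewise runs the MP observation period from V2 to the V6 injection date when V6 exists.

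**The concern.** The SAP draws the line between MP and OLEX in two places. For adverse events and observation time, the line is the first OLEX injection. For the C-SSRS, it is the visit number. V6 falls between the two: it carries an OLEX number, but its interview looks back over time before any OLEX dose.

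A laboratory value or blood pressure at V6 is a point measurement shown by visit, so a reader can see that it precedes OLEX treatment. The C-SSRS table is a cumulative at-least-once count from a look-back interview. Once V6 is included, a subject positive only at V6 cannot be told apart from one who became positive under open-label treatment.

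What is at stake is a safety display that SAP 7.5.3 ranks first among its sources on suicidality and includes to meet a regulatory requirement. Ideation beginning late in the MP and also recorded as an adverse event would be an MP TEAE under SAP 7.5.2, yet an OLEX case in the C-SSRS table if first reported at V6. The two safety displays would disagree on the period of one event, and the blinded MP display could miss it.

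**Working it through.** The documents give no figure on this point, so there is nothing to reproduce. The check sets the rules side by side and then works out the look-back from the visit windows.

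**Rules**

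| Item | MP | OLEX | Source |
|---|---|---|---|
| C-SSRS case | positive at any post-baseline visit | positive at any visit | SAP 7.5.3 |
| TEAE | from first MP injection until first OLEX injection | from first OLEX injection | SAP 7.5.2 |
| Observation time | V2 to V6 injection | from V6 injection | SAP 7.6 |

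1. V6 is an OLEX visit (SAP 3.1) and the C-SSRS is done at all OLEX visits (SAP 6.5.3), so the literal counting rule takes in V6.
2. The V6 interview precedes the V6 injection (Protocol 9.1, general rule) and looks back to the previous visit (SAP 7.5.3).
3. A V6 positive therefore refers only to time before the first OLEX dose, which the second and third rows of the table assign to the MP.
4. V10 and V14 are also pre-injection visits, but they look back only over OLEX time. The problem is confined to V6, one of 17 − 6 + 1 = 12 OLEX visit numbers.

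**Length of the look-back at V6**

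Inputs (SAP 3.1): V4 at Day 57 ± 3, i.e. Day 54 to 60; V5 at Day 99 ± 14, i.e. Day 85 to 113; injection no later than 16 weeks after the previous one, i.e. Day 1 + 112 = Day 113.

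- *V6 on a separate, later day.* The previous visit is V5. The longest gap is 113 − 85 = 28 days and the shortest is 1 day. A positive first reported here counts in the OLEX table and, because V6 is not an MP visit, not in the MP table.
- *V6 on the same day as V5, with the V5 answer carried to V6.* The look-back is that of V5, back to V4: nominally 99 − 57 = 42 days, range 85 − 60 = 25 to 113 − 54 = 59 days. One report would then appear in both tables. No text states that this carry-over applies to the C-SSRS.
- *V6 on the same day as V5, with a fresh interview at V6.* The look-back since V5 is close to zero and little or nothing is misplaced.

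**The case against.** Several points on the other side are fair.

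- **The procedure at V6 is partly inferred.** The available protocol text does not describe the C-SSRS, and the visit tables are not reproduced. That the interview precedes the injection rests on the general sentence in Protocol 9.1, and the V6-to-V17 numbering quoted from SAP 6.5.3 belongs to vital signs. This stands as a limit on certainty. However, SAP 3.1 lists V6 under OLEX independently, and nothing available exempts the C-SSRS from the general rule.
- **The cited scoring guide or the table shells might set the baseline for each period.** Neither is available. They may resolve the point, but the SAP sentence as written does not.
- **Events reported as adverse events are dated correctly.** The suicidality screen in SAP 7.5.2 works on TEAEs and so follows the injection cut. True, but that does not correct the C-SSRS table.

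A reader might infer more than the documents support:

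- *That same-day V5/V6 reports are definitely counted twice.* The footnote in Protocol 9.2 says that "the results of these assessments can be transferred from V5 to V6" but does not name this scale, and the SAP sentence using same-day data for both visits is in the efficacy section (7.1). Double counting is possible, not established.
- *That the misplaced share can be put at 42/98 = 43% of MP observation, or 42/294 = 14% on top of three 98-day OLEX cycles.* Those ratios need the carry-over just described, and reading the second as inflation of the count also needs a constant event rate. Moreover, the table counts subjects positive at least once: a subject positive at V6 and again later adds nothing.
- *That events under the mid or low dose are presented as high-dose events.* The OLEX table is also shown by MP treatment group, so the original arm is visible. By design 172/344 = 50% of subjects already received the high dose in the MP; for them the dose group would not change.
- *That the whole MP is swept in.* Only the last inter-visit interval is.

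**Conclusion.** The point holds as an error of period. As written, SAP 7.5.3 lets a positive V6 interview count as an OLEX case although it describes time that SAP 7.5.2 and 7.6 assign to the MP. When V6 is a separate visit, the same event is also left out of the MP table.

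The affected window is 1 to 28 days for a separate V6. It is nominally 42 days (25 to 59) for a same-day V6 only if the V5 answer is carried over, and close to zero if a fresh interview is held. How many subjects this touches cannot be determined: the documents give no event rate, no frequency of separate V6 visits and no size for the C-SSRS population, which is limited to subjects enrolled after amendment 1 with suitable age and cognitive state. Counts are likely to be small, so even one misplaced subject could be noticeable.

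The conclusion assumes that the general pre-injection rule applies to the C-SSRS, that V6 uses the look-back form, and that no unseen table shell or guide overrides the SAP sentence. The table is descriptive and no confirmatory result is affected. The correction is still worth making, because this is a stated rule that misassigns safety reports rather than a missing detail.

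**What to change.** In SAP 7.5.3, use for the C-SSRS the cut already used for TEAEs:

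- **MP table:** subjects with any positive post-baseline assessment up to and including the pre-injection V6 assessment, each subject counted once.
- **OLEX table:** subjects with any positive assessment after the first OLEX injection, i.e. V7 to V17. V10 and V14 remain.
- **V6:** shown in the OLEX output only as pre-OLEX status.

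Counting each subject once in the MP table also makes a same-day V5/V6 carry-over harmless. The cost is one sentence in the SAP and a changed visit filter in two tables. No new data are needed and no other analysis changes.
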